No data base lock will be performed prior to first and second interim analyses, so it is assumed that the data may not be fully monitored or queried. In addition, the datasets from immunogenicity assessments may not contain all participants' data. However, the data cuts outlined above are intended to inform additional clinical development considerations, including selection of ARCT-021 dose for booster administration and selection of final dose and schedule for ARCT-021 administration in the Phase 3 study. The data will be monitored prior to and the database will be locked after the third interim analysis to inform an interim clinical study reporting.

All available safety and immunogenicity data will be summarized. Blinded data will be shared with the SRC and unblinded data will be shared with the DSMB.

At each analysis, the DSMB will review the available data and make recommendations to the Sponsor to continue, modify, or discontinue study enrollment (if the study is enrolling participants). The DSMB will also review safety and, if available, immunogenicity data at each interim analysis.

For dose selection for Phase 3 study use, it is expected that the Sponsor will select the dose on the basis of review of available immunogenicity data and safety data (including DSMB evaluation of the benefit/risk profile). It is anticipated that if one or more vaccine groups have an acceptable safety and immunogenicity profile, the vaccine group with the smallest number of doses will be selected for future use based on the review of the Phase 2 study data. As of protocol version 4.0, the Sponsor has selected single doses of 5 µg ARCT-021 for future use in Phase 3 studies. See the IB for more detail.

LIST OF ABBREVIATIONS

Abbreviation	Definition
ACE-2	angiotensin-converting enzyme-2 receptor
AE	adverse event
AESI	adverse event of special interest
BAb	binding antibody
BMI	body mass index
CESI	clinical event of special interest
CFR	Code of Federal Regulations
CI	confidence interval
CMH	Cochran–Mantel–Haenszel
CMI	cell-mediated immune
COVID-19	Coronavirus Disease 2019
CRF	case report form
CRO	contract research organization
CSR	clinical study report
DSPC	1,2-distearoyl-sn-glycero-3-phosphocholine
DSMB	Data Safety Monitoring Board
EDC	electronic data capture
eCRF	electronic case report form
FDA	US Food and Drug Administration
FSH	follicle-stimulating hormone
GCP	Good Clinical Practice
GMC	geometric mean concentration
GMFR	geometric mean fold-rise
GMR	geometric mean ratio

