2.1. Primary Objectives and Endpoints

The primary objectives and endpoints are presented in Table 2-1 (For estimands, see [Appendix 3](#)).

Table 2-1 Primary Objectives and Endpoints

Objective(s)	Endpoint Descriptions
Primary	
• To assess the safety and reactogenicity of ARCT-021 compared to placebo for priming vaccination	Safety will be evaluated in all participants receiving at least 1 administration of study vaccine (ARCT-021 or placebo) and will be summarized for each vaccination as number and percentage of participants with: 
• Any unsolicited adverse event (AE) initiating within 28 days after each study vaccine administration, by severity and relationship to study vaccine• Any medically attended adverse event (MAAE), new onset of chronic disease (NOCD), AE leading to discontinuation/withdrawal or serious adverse event (SAE) through Early Termination• Safety laboratory assessment before and 7 days after each study vaccine administration, by toxicity grade Reactogenicity will be evaluated in all participants receiving at least a single administration of study vaccine and will be summarized for each vaccination as number and percentage of participants with: Any solicited local or systemic AE initiating within 7 days after each study vaccine administration, by toxicity grade

 To assess the neutralizing antibody responses of ARCT-021 compared to placebo for priming vaccination 	
Neutralizing antibody (NAb) responses will be evaluated in all participants receiving at least 1 administration of study vaccine (ARCT-021 or placebo).
 
 Geometric Mean Titer (GMT) measured at all time points Geometric Mean Fold-rise from baseline (GMFR); measured at all time points after baseline (= Day 0) Percentages of participants with ≥ 2- and 4-fold increase in titer from baseline (Seroconversion [SC]); measured at all time points after baseline GMT ratio (ARCT-021/placebo) measured at all time points

 To select the dose and schedule for use in the Phase 3 study in adult participants 	
Safety and reactogenicity data after each priming vaccine administration and immunogenicity response measured 28 days after each priming vaccination will be evaluated in younger (18 to < 56 years) and older (≥ 56 years) adults

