All CIs will be 2-sided and performed using a 5% significance level. No multiplicity adjustment will be made for this study where multiple treatment groups and endpoints are being evaluated.

All analyses adjusting for age group (≥ 18 to <56 years; ≥ 56 years) will use the values derived from age reported in the interactive response technology (IRT) which was used for randomization stratification.

Early termination visits will be summarized separately for the priming vaccination period and the booster vaccination period, respectively.

Analysis will be presented by study phase and study treatment group where applicable as per [Table 4-1](#) below:

Table 4-1 **Study Phase and Study Treatment Groups**

Study Phase	Study Treatment Groups	Shell Presentation of Treatment Group
Priming Vaccination	ARCT-021 7.5 µg - Placebo	A
	ARCT-021 5.0 µg - ARCT-021 5.0 µg	B
	ARCT-021 7.5 µg - ARCT-021 7.5 µg	C
	Placebo	D
Booster Vaccination	ARCT Priming - ARCT-021 Booster	E1
	Placebo Priming - ARCT-021 Booster	E2
	ARCT Priming - ARCT-154 Booster	F1
	Placebo Priming - ARCT-154 Booster	F2
	ARCT Priming - ARCT-165 Booster	G1
	Placebo Priming - ARCT-165 Booster	G2
	ARCT Priming - Placebo/No Booster	H1
	Placebo Priming - No Booster	H2
Priming Vaccination (Re-enrolled Subjects Only)	ARCT-021 7.5 µg - Placebo	A
	ARCT-021 5.0 µg - ARCT-021 5.0 µg	B
	ARCT-021 7.5 µg - ARCT-021 7.5 µg	C

For some summary tables of booster vaccination period, active boosters will be pooled, and treatment groups will be presented like the following:

Booster Vaccination	ARCT-021 7.5 µg - Placebo - ARCT Booster	A1
	ARCT-021 7.5 µg - Placebo - Placebo Booster/ No Booster	A2
	ARCT-021 5.0 µg - ARCT-021 5.0 µg - ARCT Booster	B1
	ARCT-021 5.0 µg - ARCT-021 5.0 µg - Placebo Booster/No Booster	B2
	ARCT-021 7.5 µg - ARCT-021 7.5 µg - ARCT Booster	C1
	ARCT-021 7.5 µg - ARCT-021 7.5 µg - Placebo Booster/No Booster	C2
	Placebo - ARCT Booster	D1
	Placebo - No Booster	D2

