8.2.2. Supportive Analyses of Primary and Secondary Immunogenicity Endpoints

8.2.2.1. Supportive Analyses of Estimand 2

To assess the magnitudes of the differences between the treatment groups (ARCT-021 vs. Placebo) in SARS-CoV-2 neutralizing antibody (NAbs) and SARS-CoV-2 binding antibody (BAbs) endpoints, an analysis of covariance (ANCOVA) model will be fitted to the natural log transformed neutralizing antibody titers measured against SARS CoV 2 with terms for treatment group, age group (≥ 18 to < 56 and ≥ 56 years) (stratification factor at randomization) and natural log baseline titer by each post-vaccination immunogenicity visit. No imputation of missing data will be done.

The geometric least squares mean (GLSM) and corresponding 2-sided 95% CI for the antibody titers for each treatment group will be provided by visit. The GLSM and corresponding 95% CI results in log-transformed scale estimated from the model will be back-transformed to obtain these estimates in the original scale. Geometric mean ratio (GMR), estimated by the ratio of GLSM and the corresponding 2-sided 95% CI will be provided to assess the treatment difference between ARCT-021 group vs. placebo group at each visit.

ANCOVA analyses will be performed for the priming vaccination period on mITT analysis set only.

8.2.2.2. Supportive Analyses of Estimand 3

The common difference of seropositivity and seroconversion rates and 95% CIs between each vaccine dose group and the placebo will be estimated using the Miettinen-Nurminen method with age group (≥ 18 to < 56 and ≥ 56 years) as stratification factor for each time point.

Miettinen-Nurminen analyses will be performed for the priming vaccination period on mITT analysis set only.

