9.1.2.1. Unsolicited AEs through 28 Days Post Each Vaccination

Summaries of unsolicited AEs through 28 days post each vaccination dose will be presented using the following definition:

- **Vaccination 1:** Time period from first vaccination through prior to the second vaccination for participants that received the second vaccination and through 28 days following the first vaccination for participants that did not receive the second vaccination
- **Vaccination 2:** Time period from second vaccination through 28 days following the second vaccination
- **Booster Vaccination:** Time period from booster vaccination through 28 days following the booster vaccination.

The summaries for Vaccination 1 and Vaccination 2 will be by the 4 priming vaccination treatment groups for the priming vaccination period while the summaries for booster vaccination period will be by the 8 priming-booster vaccination treatment groups and for the combined E1+E2+...+G1+G2 and H1+H2 groups (Table 4-1).

For re-enrolled subjects, the above summary for the priming vaccination phase will be repeated.

An overall summary of unsolicited AEs through 28 days post vaccination will be produced for all participants and by age group including the number and percentage of participants with any of the following (including 2 sided 95% CIs using the Clopper-Pearson method):

- Any unsolicited TEAEs
- Any severe unsolicited TEAEs
- Any unsolicited TEAEs that are treatment related

- Any severe unsolicited TEAEs that are treatment related
- Any serious TEAEs
- Any treatment-emergent MAAEs
- Any treatment-emergent NOCDs
- Any TEAEs leading to discontinuation/withdrawal
- Any TEAEs leading to death

In addition, incidence of unsolicited AEs through 28 days post each vaccination will be summarized by SOC and PT including number and percentage of participants with an event for all participants and by age group for the following:

- All unsolicited AEs
- All unsolicited AEs by severity
- All unsolicited AEs by relationship to treatment

For re-enrolled subjects, the above summaries will be repeated for the Safety set. A summary of incidence of unsolicited adverse events up to 28 days post booster vaccination with active boosters pooled will be presented.

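### Dose selection is a primary objective, yet the final analysis plans no 7.5 versus 5.0 µg estimate after Dose 1, although Groups 1 and 3 share the same 7.5 µg first injection

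*SAP*

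**What the plan says.** SAP 2.1 keeps as a primary objective "To select the dose and schedule for use in the Phase 3 study in adult participants". Its endpoint is safety and reactogenicity after each priming dose and immunogenicity 28 days after each, in both age groups.

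SAP Table 4-1 lists the active priming regimens as "ARCT-021 7.5 µg - Placebo" (A, Group 1), "ARCT-021 5.0 µg - ARCT-021 5.0 µg" (B, Group 2) and "ARCT-021 7.5 µg - ARCT-021 7.5 µg" (C, Group 3); D is placebo. The table has no column pooling A and C after Dose 1.

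For unsolicited events, SAP 9.1.2.1 states: "The summaries for Vaccination 1 and Vaccination 2 will be by the 4 priming vaccination treatment groups for the priming vaccination period". SAP 9.1 and 9.1.1 give counts and percentages by group, several with Clopper-Pearson intervals, but no between-group difference.

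For antibody, SAP 8.2.2.1 fits an ANCOVA at each visit and reports the GMR "to assess the treatment difference between ARCT-021 group vs. placebo group at each visit". SAP 8.2.2.2 estimates seroconversion and seropositivity differences between each dose group and placebo.

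On the choice itself, the Protocol Synopsis (Interim Analyses) anticipates that, if one or more groups are acceptable, "the vaccine group with the smallest number of doses will be selected for future use". It then records: "As of protocol version 4.0, the Sponsor has selected single doses of 5" µg for Phase 3. Protocol 1.6 and 7.8 repeat that selection.

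**The concern.** The objective asks a dose question, and the design holds a clean randomised answer to part of it: one 7.5 µg injection against one 5.0 µg injection, up to the pre-Dose-2 sample on Day 28. Followed exactly, the plan shows the 7.5 µg arm of that comparison as two columns and never estimates the difference.

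A single 5 µg dose was also not one of the randomised priming regimens. In the priming period it is seen only as the first 28 days of a two-dose regimen. Without a statement to that effect, Group 2 results after Day 28 could be read as support for a one-dose schedule. At stake are the completeness and precision of the answer to a primary objective. No error rate is involved, because Protocol 7.2 rules out hypothesis testing.

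**Working it through.** **1. Which groups are the same, and until when.** A, B and C receive 7.5, 5.0 and 7.5 µg on Day 0. Their second injections on Day 28 are placebo, 5.0 and 7.5 µg. Protocol Table 13-1, footnote g, requires blood to be drawn before vaccination, so the Day 28 sample precedes Dose 2. A and C are therefore one exposure for the Day 7, 14 and 28 assessments and for the Vaccination 1 adverse-event window, which SAP 9.1.2.1 closes before the second dose.

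**2. The plan's own detection figure.** SAP Table 4-2 uses 1 − (1 − R)^N. At R = 1%:
- N = 150: 1 − 0.99^150 = 0.7785.
- N = 300: 1 − 0.99^300 = 0.9510.

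Both match the table. Because A and C are both reported, the chance that a 1% event appears in at least one 7.5 µg column is already 1 − 0.99^150 × 0.99^150 = 95.1%. By the same argument it is already 77.9% within one age cohort (75 + 75). Pooling changes neither.

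**3. Precision of the contrast.** Inputs:
- 75 per group per age cohort, so 150 per group over both ages (SAP 4.2).
- SD 1.2 on the natural-log scale (SAP 4.2).
- A 10% event rate in both arms. This is an assumption; the documents give no such rate.
- No dropout, and normal approximations.

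GMR interval factor = exp(1.96 × 1.2 × √(1/n₇.₅ + 1/n₅.₀)). Risk-difference half-width = 1.96 × √(0.10 × 0.90 × (1/n₇.₅ + 1/n₅.₀)).

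| Comparison, both ages | n 7.5 : 5.0 | SE (log) | GMR factor | Half-width |
|---|---|---|---|---|
| One 7.5 µg group vs B | 150 : 150 | 0.139 | 1.31 | 6.8 points |
| A + C vs B | 300 : 150 | 0.120 | 1.27 | 5.9 points |

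The standard error falls by 1 − 0.120/0.1386 = 13.4%. Within one age cohort the GMR factor goes from 1.47 (75 : 75) to 1.40 (150 : 75).

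In the ANCOVA the contrast is the mean of A and C minus B. With equal groups its variance is σ²[¼(1/150 + 1/150) + 1/150] = σ²(1/300 + 1/150), the same as pooling. No refitting is needed.

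**4. A column that would be mixed.** SAP 4.5 assigns safety and reactogenicity groups by the whole two-dose sequence. Someone randomised to two 5.0 µg doses who received placebo at Dose 2 goes into the 7.5 µg single-dose group. In a Dose 1 table that counts a 5.0 µg first dose as 7.5 µg. The two exchanges between the 7.5 µg single-dose and two-dose groups do not matter once A and C are pooled.

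**The case against.** The strongest reply is that the decision is past. Protocol 1.6 attributes it to the Phase 1/2 study and interim data, SAP 1 says the interim analyses had separate plans, and the Version 6.0 amendment summary says the sponsor intends no further studies of ARCT-021. This stands in part. Those interim plans may have pooled the groups or compared doses, so the gap is shown only for the protocol and this SAP. The objective nevertheless remains in this SAP, and the final report has to address it.

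Second, most of the information is already there. Events can be summed over A and C, and the ANCOVA gives a least-squares mean for every group, so the 7.5/5.0 ratio is one division away. That is right for point estimates. It does not supply an interval for the ratio or the risk difference, and in a study whose stated purpose is estimation the interval is the useful part. Tabulating by randomised regimen is a legitimate convention and should stay.

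A reader might also infer several stronger things that the documents do not support:
- *That pooling improves the detection of rare events.* It does not, as step 2 shows.
- *That the sponsor's choice rested on the missing contrast.* Protocol 1.6 cites the seroconversion rate and reactogenicity profile of single 5 µg doses in absolute terms. Protocol 1.5 offers only a tentative remark that Grade 3 solicited events may be slightly more frequent at 7.5 µg. A link is a plausible inference, not a stated fact.
- *That the selection broke a rule.* The fewest-doses sentence is an expectation, and the next sentence openly records the choice.
- *That Group 2 as first randomised is the only randomised 5.0 µg first-dose evidence.* Re-enrolled placebo participants are also randomised to that regimen, although they are summarised separately and their antibody data are only listed.

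**Conclusion.** The point holds for the two documents reviewed. They plan no 7.5 versus 5.0 µg estimate with an interval after Dose 1, and they keep one exposure in two columns, while dose selection remains a primary objective. The loss of precision is modest: about 13% in standard error, or 1.31 to 1.27 on the GMR factor and 6.8 to 5.9 points on a risk difference. The larger gap is that the contrast is not estimated at all.

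These figures assume planned numbers, no dropout, SD 1.2 without covariate adjustment and a 10% event rate. Protocol 1.5 reports 579 enrolled against about 600 planned, so realised intervals would be slightly wider on that account. This is a worthwhile low-cost improvement. It does not show that the planned analyses are wrong or that the dose choice was unsound.

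**What to change.** 1. Keep the four-group tables. In SAP Table 4-1 add a Dose 1 presentation by the dose actually received at Dose 1: 7.5 µg (A + C), 5.0 µg (B) and placebo (D). Use it for solicited events within 7 days of Dose 1, Vaccination 1 unsolicited events, Day 7 laboratory grades, and Day 14 and Day 28 pre-Dose-2 antibody.
2. From the planned Day 14 and Day 28 ANCOVA, report the 7.5/5.0 GMR (A and C combined versus B) with 95% CI. Add a 7.5 minus 5.0 risk difference with 95% CI for Dose 1 solicited events of Grade 3 or higher. The mITT model uses assigned groups, so state the grouping basis of each output.
3. Label these as descriptive additions made after the interim analyses, since SAP 10 has unblinded interim data going to the sponsor.
4. Reconcile the SAP 4.5 row described in step 4, so that a 5.0 µg first dose is not counted as 7.5 µg.
5. In the report, state that a single 5 µg dose was not a randomised priming regimen. Its priming-period evidence is Group 2, and separately participants re-enrolled into Group 2, up to the Day 28 dose; later Group 2 data are two-dose data. Note that group E2 (placebo-primed, ARCT-021 5.0 µg at Day 208) offers follow-up beyond 28 days after one active dose, but with the lyophilized formulation.

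The cost is some SAP wording, a few table columns and two contrasts from data already collected. The report would also make a more limited statement about the selected regimen.
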